11.8.1 Solicited Local AEs

The solicited local symptoms erythema, swelling, induration, pruritus and pain at the injection site are to be documented in the memory aid by the subjects.

Assessment of Intensity

Injection site erythema, swelling, and induration will be assessed based on the longest diameter as measured by the subject in mm and recorded in the memory aid. Subjects are asked to document the solicited local AEs in the memory aid. For injection site erythema, injection site swelling, and injection site induration, subjects are asked to record longest diameters; for injection site pruritus and injection site pain, subjects are asked to record level of severity as described in Table 2 below.

ABNCoV2-03

Edition 8.0

MedDRA coded Preferred Term **Grading for Analyses Grading Assessed at Diary Local Adverse Events** Review Severity Measure^a Grade **Severity Measure** Grade Injection site erythema, Injection 0 0 cm 0 0 mm site swelling, and Injection site 1 2.5 - 5 cm1 <30 mm induration^b (longest diameter) \geq 30 – <100 mm 5.1 - 10 cm2 2 3 >10 cm 3 ≥100 mm 0 Injection site pruritus Absent Same as assessed at diary review 1 Mild 2 Moderate 3 Severe Absent Injection site pain Same as assessed at 0 Painful on touch diary review 1 2 Painful when limb is moved 3 Spontaneously painful/prevents normal activity

Table 2Grading of Local Symptoms from the Subject's Memory Aid

^a Per FDA "Guidance for Industry: Toxicity Grading Scale for Healthy Adult and Adolescent Volunteers Enrolled in Preventive Vaccine Clinical Trials", September 2007. Available at https://www.fda.gov/media/73679/download.

^b Per FDA guidance, injection site swelling and induration are combined (i.e., injection site swelling/induration).

Assessment of Causality

Solicited local AEs are defined as being related to the vaccine.

11.8.2 Solicited General AEs

The solicited general symptoms body temperature, headache, myalgia, nausea, chills and fatigue are to be documented in the memory aid by the subjects.

Assessment of Intensity

Subjects are asked to document the solicited general AEs in the memory aid. Subjects are asked to record temperature and severity of symptoms as described in Table 3 below. In the subject's memory aid, the grading of symptom intensity is described in basic, easily understood language based on the following descriptions:

ABNCoV2-03

Edition 8.0

daily activity

MedDRA coded Preferred Term **Grading for Analyses Grading Assessed at Diary General Adverse Events** Review Grade **Severity Measure** Grade Severity Measure^a Body temperature (oral)^b 0 <38.0°C (<100.4°F) 0 <37.5°C (<99.5°F) 1 1 ≥37.5 – <38.0°C 38.0 - 38.4°C $(100.4 - 101.1^{\circ}F)$ $(\geq 99.5 - < 100.4^{\circ}F)$ 2 38.5 – 38.9°C 2 \geq 38.0 - <39.0°C $(101.2 - 102.0^{\circ}F)$ (≥100.4 – <102.2°F) 3 3 39.0 - 40°C \geq 39.0 - <40.0°C $(102.1 - 104^{\circ}F)$ $(\geq 102.2 - <104.0^{\circ}F)$ 4 4 >40°C (>104°F) ≥40.0°C (≥104.0°F) Headache, Myalgia, Nausea, Chills 0 None Same as assessed at and Fatigue diary review 1 Mild: easily tolerated, minimal discomfort and no interference with daily activity 2 Moderate: Some interference with daily activity 3 Severe: Prevents

Table 3	Grading of General	Symptoms from the	e Subject's Memory Aid
1 4010 0	Grading of General	Symptoms nom en	c Subject S memory mu

^a Per FDA "Guidance for Industry: Toxicity Grading Scale for Healthy Adult and Adolescent Volunteers Enrolled in Preventive Vaccine Clinical Trials", September 2007. Available at https://www.fda.gov/media/73679/download.

^b Pyrexia is defined as oral temperature ≥38.0°C (≥100.4°F), which is fever Grade ≥1 by FDA grading and oral temperature Grade ≥2 as assessed at diary review.

Assessment of Causality

Causal relationship between solicited general AEs and the vaccine will be assessed by the investigator using the same categories as for unsolicited AEs (see Section 11.7).

11.9 Adverse Events of Special Interest

11.9.1 General AESI Definitions

For this trial, AESIs are defined according to the following lists of AESIs available:

 Brighton Collaboration SPEAC – Safety Platform for Emergency vACcines (SPEAC) Project generated list of AESI for safety monitoring (accessible via https://brightoncollaboration.us/covid-19/). This list is updated on a quarterly basis and the current effective list of AESIs is applicable for this trial. Links to the Brighton

ABNCoV2		Clinical Trial Protocol
ABNCoV2-03	Edition 8.0	

Collaboration's case definitions for AESIs applicable for COVID-19 vaccine trials are provided in Appendix 3.

- 2. ACCESS Project List of Adverse events of special interest and case definitions (accessible via http://www.encepp.eu/documents/DraftReport.pdf).
- 3. CBER Surveillance Program List of Adverse Events of Special Interest (accessible via https://www.bestinitiative.org/wp-content/uploads/2021/02/C19-Vaccine-Safety-AESI-Background-Rate-Protocol-FINAL-2020.pdf).
- 4. Additionally, confirmed COVID-19 infection is also considered as AESI. Confirmed COVID-19 infection requires laboratory confirmation of SARS-CoV-2 using reverse transcription PCR methods (ECDC, 2020).

BN has compiled an all-inclusive list of AESIs based on references provided above, which is part of investigator training materials.

For timelines for reporting and follow-up of AESIs, see Section 11.14.1. The same timelines and reporting processes as for SAEs are applicable.

11.9.2 Myocarditis and Pericarditis

Myocarditis and pericarditis are a subset of AESIs of particular interest. Postmarketing data from mRNA vaccine recipients have demonstrated increased risks of myocarditis and pericarditis in males under the age of 40 years following a second dose of mRNA vaccine. Cases have been reported in older males and in females as well, and also following other doses. Available data from short-term follow-up suggest that most individuals have had resolution of symptoms with conservative management, although information is not yet available about potential long-term sequelae.

The spike (S) protein antigen can induce antibodies to SARS-CoV-2 spike glycoproteins that cross-react with myocardial contractile proteins, including myocardial α -myosin heavy chain (Vojdani and Kharrazian, 2020). In contrast to the currently licensed COVID-19 vaccines, the ABNCoV2 candidate vaccine does not contain the full-length S protein of the SARS-CoV-2 virus, but specifically the receptor binding domain (RBD) of the S protein. However, as the pathomechanism for myocarditis or pericarditis following COVID-19 vaccination is not fully understood, and the specific role of the RBD remains unclear, precautionary measures will be implemented for this trial.

Symptoms of myocarditis or pericarditis include chest pain, shortness of breath, or feelings of having a fast-beating, fluttering, or pounding heart, with onset of symptoms most commonly reported within a few days following vaccination. While some cases required intensive care support, available data from short-term follow-up suggest that symptoms resolve in most individuals with conservative management. Information is not yet available about potential long-term sequelae. Subjects will receive educational materials explaining the symptoms of

Bavarian Nordic

ABNCoV2-03

Edition 8.0

myocarditis and pericarditis and instructing them to seeking medical attention if they occur. Subjects reporting acute chest pain, shortness of breath, palpitations, or other signs or symptoms of myocarditis or pericarditis within 4 to 6 weeks after vaccination will be referred to a cardiologist for evaluation and management. Cases of myocarditis and pericarditis will be followed until resolution of symptoms and abnormal test findings.

Determination of myocarditis and pericarditis will be performed based on the case definitions and guidelines from the Brighton Collaboration Myocarditis/Pericarditis Working Group (Sexson Tejtel et al., 2022). Reference to the publication of these case definitions is provided in Appendix 3. Cases of myocarditis or pericarditis occurring in temporal association with vaccination will be considered as potentially related, unexpected, and serious (as important medical events, even if other seriousness criteria are not met). These will be included in expedited reporting for the trial.

An adverse event follow-up questionnaire for cardiac events (Appendix 4) will be used during the study.

The DMC will review cases of myocarditis and pericarditis, with details as to the timelines for review and ad-hoc meetings to be described in the DMC charter (Section 13.3.1). In addition, recommendations for pausing or halting the trial will be in line with the stopping rules described in Section 13.3.2.

11.10 Confirmed COVID-19 Infection with Severe Manifestations or Resulting in Critical Illness

All cases of COVID-19 disease with severe manifestations or resulting in critical illness will be reviewed periodically by the DMC.

Severe COVID-19 in adults is defined as dyspnea, a respiratory rate of 30 or more breaths per minute, a blood oxygen saturation of 93% or less, a ratio of the partial pressure of arterial oxygen to the fraction of inspired oxygen (Pao2:Fio2) of less than 300 mm Hg, or infiltrates in more than 50% of the lung field (Berlin et al., 2020). Critical illness is defined as respiratory failure, septic shock, and/or multiple organ dysfunction (NIH, 2021).

11.11 Safety Laboratory Measurements

The intensity of laboratory/systemic toxicities measured quantitatively will be graded according to the Toxicity Grading Scale for Healthy Adult and Adolescent Volunteers Enrolled in Preventive Vaccine Clinical Trials (FDA, 2007). The laboratory values provided in this toxicity grading scale serve as guidelines and are dependent upon institutional parameters. Institutional specific toxicity gradings will be included in site specific manuals as needed.

Safety laboratory measurements are obtained at Screening and Visit 3 and at any other visit(s) if clinically indicated. For subjects who discontinued during the trial and are coming for the EAP

Bavarian Nordic

ABNCoV2		Clinical Trial Protocol
ABNCoV2-03	Edition 8.0	

visit so that final safety data can be collected, safety labs may be done at this time. Safety laboratory parameters to be evaluated are:

Hematology:

Red blood cell count, hemoglobin, total and differential white blood cell count (WBC), platelet count, hematocrit, mean corpuscular/cell volume (MCV), mean corpuscular/cellular hemoglobin (MCH), mean corpuscular hemoglobin concentration (MCHC) and red blood cell distribution width (RDW) are routinely performed as part of the complete blood cell count and will be included in the laboratory report.

Serum chemistry:

Total bilirubin, ALP, AST, ALT, serum creatinine, sodium, potassium, calcium, c-reactive protein.

Pregnancy test:

A β -human choriogonadotropin (β -HCG) pregnancy test will be conducted for all WOCBP at screening, prior to vaccination, and at EAP. At screening a serum β -HCG pregnancy test will be performed; other pregnancy tests will be conducted as urine β -HCG tests.

Virology:

The following parameters will only be evaluated during the screening period for assessment of inclusion/exclusion criteria:

- Human immunodeficiency virus antibody (anti-HIV)
- Hepatitis B surface antigen (HbsAG)
- Hepatitis C antigen (HCV)

SARS-CoV-2 Testing:

Testing by PCR for SARS-CoV-2 infection will be done at screening. It also will be performed at any time throughout the trial starting after vaccination if clinically indicated (e.g., in the presence of typical COVID-19 symptoms; see the trial schedule, Section 1.4).

Positive SARS-CoV-2 infections, whether detected by testing within the trial or outside the trial, should be reported as AESIs (see Section 11.10).

ABNCoV2-03

Edition 8.0

11.12 Cardiac Assessment

A standard 12-lead ECG will be required at screening. An ECG may be performed at any other visit if clinically indicated. The investigator will assess the clinical significance for abnormal ECGs.

11.13 Pregnancy

As per inclusion criteria, WOCBP must have a negative serum pregnancy test at screening and a negative urine pregnancy test at randomization. In addition, WOCBP and male subjects who are sexually active with WOCBP must have used an acceptable method of contraception for 30 days prior to the trial vaccination, must agree to use an acceptable method of contraception during the trial, and must avoid pregnancy for at least 30 days after the vaccination. Nevertheless, IMP-exposed pregnancies cannot be excluded with certainty. Subjects who become pregnant prior to vaccination will be excluded from the trial and are regarded as screening failure. Subjects who become pregnant during the active trial phase (up to and including 1 month [minimum 28 days] after receiving trial vaccine) may continue trial procedures at the discretion of the investigator. All reports, where the embryo or fetus may have been exposed to the IMP will be followed-up until delivery to collect information on the outcome of the pregnancy (see Section 11.14.3).

Subjects will be instructed to notify the investigator if it is determined (also after completion of the trial) that they became pregnant during the trial.

11.14 Reporting

11.14.1 Reporting of SAEs and AESIs

All SAEs (collection starts at signing of ICF) and AESIs (collection starts upon vaccination) occurring throughout the entire course of the trial, to include the active trial and follow-up period, must be entered in the eCRF within 24 hours of awareness by the investigators, which triggers an autogenerated output to the drug safety department of ______, the contract research organization (CRO) for this trial.

In case the eCRF is unavailable, the SAE/AESI must be reported to **by** telephone or fax within 24 hours of becoming aware of the SAE and/or AESI as follows:

ABIVEO V2		
ABNCoV2-03	Edition 8.0	
SAE/AESI Hotline:		
• •		
SAE/AESI Hotline Fax:		
•		

The investigator should not delay reporting because of missing information. Nonetheless, the report should be as complete as possible. This initial report should include, at a minimum, sufficient information to permit identification of the following:

- The reporter (investigator's name and contact information)
- The subject
- Involved trial medication
- AE(s)
- Seriousness criterion
- Date of onset

is responsible for expedited reporting to the involved regulatory authorities according to applicable laws and guidelines, and for safety report distribution to participating investigators, IECs or IRBs and Human Research Protection Offices.

Regulatory authorities will be notified as soon as possible but no later than 7 days after date of first receipt of fatal or life-threatening SUSAR (Suspected Unexpected Serious Adverse Reaction) with an at least possible relationship to the IMP and no later than 15 days after knowledge of any non-fatal or non-life-threatening SUSAR.

11.14.2 Reporting of MAAEs

All MAAEs will be collected for the trial duration, including the follow-up period. MAAEs must be entered in the eCRF within 24 hours of awareness by the investigators. If an MAAE is considered serious or meets criteria for an AESI, reporting procedures in Section 11.14.1 are to be followed.

11.14.3 Reporting of Pregnancies

If a subject becomes pregnant during the active trial phase (up to and including 1 month [minimum 28 days] after receiving the trial vaccination), this must be reported to within 24 hours of the investigator becoming aware of the event (Section 11.13).

ABNCoV2Clinical Trial ProtocolABNCoV2-03Edition 8.0

A pregnancy will be followed to term, any premature terminations reported, and the health status of the mother and child including date of delivery and the child's sex and weight will be reported by the investigator to **see as soon as possible**.

Any event during pregnancy fulfilling the criteria for an SAE or AESI will be reported to (see Section 11.14.1). However, hospitalization for delivery is a prospectively planned hospitalization and is not considered a SAE, per se.

12 Statistical Considerations

12.1 Randomization Procedure and Blinding Consideration, Part A Only

At Visit 1, subjects enrolled in Part A of the trial will be randomized in a 1:1 ratio to receive vaccination with a single 100 μ g dose of ABNCoV2 or a 30 μ g adult dose of Comirnaty, stratified by age (<65 years versus \geq 65 years) and prior vaccination regimens.

Randomization strata in Cohort 1 include the following prior vaccination regimens, completed at least 3 months prior to trial vaccination: 1) 2 doses of mRNA vaccine (Comirnaty or Spikevax), 2) 1 dose or 2 doses of adenovirus-based vaccine (Vaxzevria or Janssen COVID-19 Vaccine), 3) 1 dose of adenovirus-based vaccine followed within 3 months by 1 dose of mRNA vaccine, and 4) other authorized primary vaccination regimen, if applicable.

Randomization strata in Cohort 2 include the following prior vaccination regimens, completed at least 3 months prior to trial vaccination: 1) 2 doses of mRNA primary vaccines plus 1 booster dose of mRNA vaccine (Comirnaty or Spikevax), 2) 1 dose or 2 doses of adenovirus-based primary vaccines (Vaxzevria or Janssen COVID-19 Vaccine) plus 1 booster dose of mRNA vaccine, and 3) other authorized primary vaccination and boost vaccination combinations.

Randomized assignments for subjects will be performed via an interactive voice or web response system (IVRS/IWRS) after confirmation of subject's eligibility as specified in Section 1.3.

To minimize the potential for bias, site personnel and subjects are blinded to vaccination assignment. Additionally, the BN and CRO study teams and statistical programming team will not have unblinded data until database lock/freeze for the primary analyses.

12.2 Sample Size Calculation

12.2.1 Part A

The primary and key secondary analyses will be tested in the randomized, double-blind component of the trial (Part A) in both Cohort 1 and Cohort 2. Two non-inferiority tests will be performed. Therefore, the sample size calculation is based on a one-sided, 0.0125 type I error, α ,

ABNCoV2-03

to control for both tests. This will maintain the trial-wide α at 0.025 for the one-sided null inferiority hypotheses.

Based on data from the ABNCoV2 phase 2 trial, we assume the common standard deviation to be 0.52 for log_{10} transformed neutralizing antibody titers in both the ABNCoV2 and Comirnaty arms. The test of non-inferiority of ABNCoV2 compared with Comirnaty will be performed by comparing the lower end of the 97.5% CI with a non-inferiority margin of 0.67 in the ratio of neutralizing antibody GMTs between the two groups. We further assume a 10% non-evaluable rate due to dropouts or invalid samples. With an evaluable sample size of 450, a one-sided test with an α of 0.0125 will have approximately 90% power to reject the null hypothesis that ABNCoV2 is inferior to Comirnaty.

A minimum sample size of 400 evaluable subjects will be required for the non-inferiority hypothesis test to be performed for the primary endpoint within each cohort. In the event the evaluable sample size is as low as 400, the power to reject the null hypothesis that ABNCoV2 is inferior to Comirnaty is approximately 86%. In the event that the minimum sample size is not met in one of the cohorts regardless of recruitment effort, data from the cohort will be summarized descriptively and will be integrated in the combined-cohort analyses.

For the key secondary analyses, the number of hypothesis tests to be performed will depend on the number of VOCs of interest circulating at the time of the trial. VOCs will only be formally tested sequentially in the separate Part A cohorts and in the 2 cohorts combined. Discussion of the gatekeeping procedures with regards to the multiple hypothesis tests for the key secondary endpoints is in Section 12.3.

12.2.2 Part B

The sample size for Part B is not based on formal statistical hypothesis testing, but rather on the number of subjects exposed to ABNCoV2 considered adequate for safety population analyses and may be adjusted depending on enrollment in Part A. A total of 3000 subjects (for example, 2500 from Part B plus 500 from Part A who will receive ABNCoV2) would allow for 95% power to detect an AE with an incidence rate as low as 0.1%.

The immunogenicity subset in Part B will consist of approximately 200 to 250 subjects in each cohort. This subset sample size is based on feasibility alone, i.e., the number of participating sites and consenting subjects.

12.3 Multiplicity

The hypothesis test of noninferiority of ABNCoV2 to Comirnaty in terms of neutralizing antibody titers for SARS-CoV-2 will be performed in Part A in up to 2 cohorts. A Bonferroni correction will be used to control the trial-wide type I error of $\alpha = 0.025$, one-sided. In the event a cohort does not meet the requirement of 400 evaluable subjects for the primary endpoint analysis, summaries for the under-enrolled cohort will be considered purely descriptive.

ABNCoV2-03

The key secondary endpoints, ratios of GMTs for the VOCs at 2 weeks after trial vaccination, will be formally tested in Part A for non-inferiority of ABNCoV2 to Comirnaty only in the cohort(s) in which the primary success criterion is met. If the primary success criterion is met in only one cohort, VOCs will be formally tested in that cohort only. A Bonferroni adjustment will be used such that each VOC non-inferiority hypothesis will be tested at the α =

 $\frac{0.025}{number of VOCs tested}$ level. For example, if 3 VOCs are tested, each test will be performed at the α = 0.0083 level such that success would require the lower confidence limit of a 98.3% CI to be at least 0.67. In the event that success criteria are met for both Cohort 1 and Cohort 2, the number of tests will multiply, and thus non-inferiority hypothesis will be tested at the α =

 $\frac{0.0125}{number of VOCs tested}$ level so that the overall type I error rate will be no more than 5%.

12.4 Variables

Endpoint variables are provided in Section 5.

12.5 Analysis Populations

The Safety Analysis Set for all safety endpoints and population-level summaries includes all subjects who received a trial vaccination with either ABNCoV2 or Comirnaty.

The Immunogenicity Analysis Set for immunogenicity endpoints includes all subjects who are in the Safety Analysis Set, have at least a baseline and 1 post-vaccination neutralizing antibody titer result, have not tested positive for SARS-CoV-2 infection, and have not received a booster outside of the trial within 2 weeks of trial vaccination.

12.6 Primary Analysis

12.6.1 Primary Estimand

The primary variable of interest is the subjects' neutralizing antibody titers against the SARS-CoV-2 index virus measured at 2 weeks after trial vaccination in each Part A cohort, and the variable will be summarized as the ratio of GMTs for ABNCoV2 compared to Comirnaty in subjects meeting the immunogenicity analysis set definition.

The planned primary analysis will be conducted in each of the Part A cohorts, and the null hypothesis of inferiority will be rejected if the ratio of GMTs is within the non-inferiority margin of 0.67, i.e., the lower limit of the 2-sided 97.5% CI of the GMT ratio is \geq 0.67.

ABNCoV2		Clinical Trial Protocol
ABNCoV2-03	Edition 8.0	

The following are considered intercurrent events:

- 1) A positive test for SARS-CoV-2 infection prior to Visit 3 (12 to 16 days after vaccination), by PCR and
- 2) Discontinuation from the trial due to AEs.

For the primary estimand, the second intercurrent event is not considered as having an impact on the SARS-CoV-2 neutralizing antibody levels and therefore the "treatment policy" strategy will be used. Exposure to the virus can have significant effect on SARS-CoV-2 neutralizing antibody levels, and thus subjects who develop intercurrent infections will be excluded from the primary analysis. This is equivalent to the "while on treatment" strategy. Prior to database lock, a data review meeting will determine if any other intercurrent events (e.g., protocol violations) would affect the primary immunogenicity outcome and should result in exclusion of data points from the primary analysis. Strategies to handle these additional intercurrent events will be determined in a blinded fashion.

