7.2 Subject Discontinuation

A subject may be discontinued early from the active trial phase or the overall trial for different reasons. Reasons for early discontinuation of a subject may include, but are not limited to:

- Clinical need for or receipt of concomitant or ancillary therapy not permitted in the trial as outlined in Section 11.4.
- Subject's receipt of an approved booster vaccination for SARS-CoV-2 outside the protocol.
- Subject's request to discontinue (withdrawal of consent to participate).
- Subject unwilling or unable to comply with trial requirements.
- Any reason that, in the opinion of the investigator, requires or supports early discontinuation of a subject.

Each subject has the right to terminate their trial participation completely at any time for any reason, and the investigator may also terminate a subject's trial participation. Subjects whose trial participation is terminated during the active trial phase of either Part A or Part B should undergo a concluding end of active phase (EAP) visit, including safety laboratory testing and pregnancy test for women of childbearing potential (WOCBP). The subject has the right to refuse the EAP visit; however, the clinical trial site (CTS) should make every effort to collect any safety data possible for the subject. If the subject is willing, the 2-month follow-up (FU) phone call (FU1), the 3-month FU visit (FU2), and/or the 6-month visit (FU3) should still be performed to collect

ABNCoV2		Clinical Trial Protocol
ABNCoV2-03	Edition 8.0	

any potential SAEs/AESIs which occurred after vaccination. Subjects who discontinue after receiving trial vaccine will not be replaced.

8 Schedule of Procedures by Visit

The trial procedures will be conducted according to the trial procedure schedule (Section 1.4) and as described on the following pages. Visits must be scheduled within the protocol-allowed visit windows.

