### Primary Estimand

The primary variable of interest is the subjects' neutralizing antibody result against the SARS-CoV-2 index virus measured at 2 weeks after trial vaccination in each Part A cohort, and the variable will be summarized as the ratio of geometric means for ABNCoV2 compared to Comirnaty in subjects meeting the Immunogenicity Analysis Set (IAS) definition.

The planned primary analysis will be conducted in each of the Part A cohorts, and the null hypothesis of inferiority will be rejected if the ratio of GMTs is within the non-inferiority margin of 0.67, i.e., the lower limit of the 2-sided 97.5% CI of the GMT ratio is  $\geq 0.67$ .

The following are considered intercurrent events:

1. Development of COVID-19 symptoms and having a positive test for SARS-CoV-2 infection prior to Visit 3 (12 to 16 days after vaccination) by PCR or other testing method,

2. Administration of a booster for SARS-CoV-2 prior to Visit 3, and
3. Discontinuation from the trial due to AEs.

For the primary estimand, the third intercurrent event is not considered as having an impact on the SARS-CoV-2 neutralizing antibody levels and therefore the “treatment policy” strategy will be used. Exposure to the virus or receiving another booster vaccine can have significant effect on SARS-CoV-2 neutralizing antibody levels, and thus subjects who develop intercurrent infections will be excluded from the primary analysis. This is equivalent to the “while on treatment” strategy. Prior to database lock, a data review meeting will determine if any other intercurrent events (e.g., protocol violations) would affect the primary immunogenicity outcome. Strategies to handle these additional intercurrent events will be determined in a blinded fashion.

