#### 4.2.3.1. Sensitivity using Multiple Imputation for the Safety Analysis Set

Because the window between vaccination and the primary endpoint measurement is short, the number of subjects with missing data due to intercurrent events or protocol deviations substantially affecting the immunogenicity results is expected to be small. If >5% of data are missing despite the short window, missing values will be imputed via the multiple imputation (MI) method as a sensitivity analysis using the Safety Analysis Set. Missing values will be assumed to be missing at random, such that the reason for the missing value is not dependent on the result itself. As the MI procedure will be performed on the Safety Analysis Set, regardless of protocol deviations, neutralizing antibody results after vaccination that are out of window will be included rather than imputing a “missing” value for full accounting of the available data. Inclusion of serum samples collected out of window will follow the method used for the Sensitivity Analysis using the Safety Analysis Set.

The MI sensitivity analyses will be performed separately for each Part A cohort due to the different background characteristics.

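### For Part A subjects who discontinue due to an AE before Visit 3, the treatment-policy strategy is not backed by collection of the Week 2 titer

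*Protocol*

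**What the plan says.** Both documents list discontinuation from the trial due to AEs as an intercurrent event and assign it to treatment policy. Protocol 12.6.1 gives as the reason that "the second intercurrent event is not considered as having an impact on the SARS-CoV-2 neutralizing antibody levels". The Primary Estimand text in SAP 1.1 lists an outside booster as one more event and otherwise says the same: "the third intercurrent event is not considered as having an impact on the SARS-CoV-2 neutralizing antibody levels". The primary variable is the index-virus neutralizing titer 2 weeks after vaccination, and the scheduled visit for it is Visit 3 (days 12 to 16).

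Protocol 7.2 sets out what follows early termination: "Subjects whose trial participation is terminated during the active trial phase of either Part A or Part B should undergo a concluding" EAP visit, with safety laboratory and pregnancy tests. The subject may refuse it. Willing subjects then have FU1, FU2 and/or FU3, to pick up SAEs and AESIs. Visit 3 is not mentioned.

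The trial schedule and Protocol 8.2.4 place a Part A serum draw at Visit 4/EAP. SAP 4.1.5 allows that visit to come early for a subject who withdraws.

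The primary model (Protocol 12.6.2, SAP 4.2.2) compares Week 2 log10 titers, with age and baseline titer as covariates and no imputation. Multiple imputation (MI) is a sensitivity analysis only. Protocol 12.6.3 applies it to any missing data; SAP 4.2.3.1 applies it only "If >5% of data are missing despite the short window".

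**The concern.** Treatment policy means that the Week 2 titer is used regardless of discontinuation, so someone has to draw it after discontinuation. Because the single dose is given on Day 1, there is no continuing treatment to stop; what leaving early changes is whether the endpoint is measured. If nobody asks for the sample, a cooperative subject can attend the EAP visit and every follow-up contact, be counted as having completed the trial (SAP 4.1.5 and 4.6.1), and still contribute nothing to the primary comparison.

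These subjects leave because of AEs. If early reactogenicity differs between the two vaccines, the loss could differ by arm, and if it is related to immune response, the GMT ratio could shift. The documents establish neither link. The certain cost is that the clinical study report would claim an estimand strategy that data collection does not support.

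**Working it through.** **Step 1. Follow the subject through the plan.**

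| Discontinuation due to an AE | What the plan yields | Week 2 value in the primary model |
|---|---|---|
| After Visit 3 | Week 2 titer already drawn | Yes; treatment policy works as stated |
| Before Visit 3, EAP visit on days 12-16 | Part A serum titer; nucleocapsid test not scheduled at EAP | No rule either way |
| Before Visit 3, EAP visit outside days 12-16 | Part A serum titer, out of window | None; usable only in Safety Analysis Set sensitivity analyses |
| Before Visit 3, all sampling refused | Nothing | None under any rule |

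The Immunogenicity Analysis Set (Protocol 12.5) needs a baseline and any one post-vaccination titer. A subject with a Visit 2 titer can therefore stay in the set and yet be absent from the Week 2 model. The problem sits in rows two and three.

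**Step 2. Reproduce the planned power.** Protocol 12.2.1 says that "the sample size calculation is based on a one-sided, 0.0125 type I error", that "we assume the common standard deviation to be 0.52" on the log10 scale, and that the test is made "with a non-inferiority margin of 0.67 in the ratio of neutralizing antibody GMTs between the two groups". It states that 450 evaluable subjects "will have approximately 90% power to reject the null hypothesis that ABNCoV2 is inferior to Comirnaty", and about 86% power with 400. The true ratio is not stated; 1.0 is assumed here.

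- Margin: -log10(0.67) = 0.1739.
- Standard error of the difference, 1:1 allocation: 0.52 × √(4/N).
- Power: Φ(0.1739/SE - 2.2414).
- N = 450: SE = 0.0490; Φ(3.548 - 2.241) = 90.4%.
- N = 400: SE = 0.0520; Φ(3.345 - 2.241) = 86.5%.

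Both stated figures reproduce, and neither is in dispute. The calculation is per cohort, so it still applies now that SAP 2.1 limits formal testing to Cohort 2.

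**Step 3. Cost in power.** The documents give no rate of AE discontinuation before Visit 3, so a range is assumed. Taking these losses from 450, although the 10% non-evaluable allowance is meant to cover dropouts already:

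| Assumed loss | Evaluable N | Power |
|---|---|---|
| 0.2% | 449.1 | 90.4% |
| 1% | 445.5 | 90.1% |
| 2% | 441.0 | 89.8% |
| 5% | 427.5 | 88.8% |
| 10% | 405.0 | 87.0% |

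**Step 4. Possible shift in the GMT ratio.** If an excess share d is lost in one arm and those lost differ from the rest by Δ on the log10 scale, the log10 ratio moves by d × Δ. The direction is unknown.

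- Δ = 0.30 (2-fold), d = 2%: 0.02 × 0.30 = 0.006; 10^0.006 = 1.014, a 1.4% shift. That is 0.006/0.1739, about 3% of the margin.
- Δ = 0.52 (1 SD): d = 0.2%, 1%, 2%, 5% gives shifts of 0.2%, 1.2%, 2.4%, 6.2%.
- A 5% shift needs a one-sided loss of about 4% at 1 SD, or about 8% at 0.5 SD.

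**Step 5. Can the SAP's MI trigger miss an imbalance?** With 10% lost in one arm and 0% in the other, overall loss is (10% + 0%)/2 = 5%, which is not more than 5%, so the SAP runs no MI. At Δ = 0.30 the shift is 0.10 × 0.30 = 0.03; 10^0.03 = 1.07, or 7%. This is an extreme case: it puts the same 10% that the plan allows for all causes into one arm.

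**The case against.** The strongest reply is that Protocol 7.2 is silent on Visit 3 and does not rule it out. The EAP visit carries a Part A serum draw and may fall on days 12 to 16. Leaving the trial can mean leaving completely, so some values will be missing whatever 7.2 says. The plan also has sensitivity analyses that reach these subjects: MI for any missing data in Protocol 12.6.3; a Safety Analysis Set analysis without a threshold in SAP 4.2.3, with out-of-window titers included under 4.2.3.1; and a fold-rise summary in SAP 4.2.6 that counts missing values without an earlier response as non-responders. Finally, the SAP, dated 19 May 2023, says in Appendix 2 that enrollment has completed. Adding 14 days of screening and 16 days to Visit 3 gives 18 June 2023, before Edition 8.0 of 30 June 2023, leaving aside any re-screened subjects.

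Most of this stands, and it rules out several stronger readings that a reader might infer:

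- That the protocol skips Visit 3, so that the titer is never collected. It only fails to ask for it, and an early EAP draw may supply one.
- That all AE discontinuations are affected. Only those before Visit 3 are.
- That missing values are imputed only above 5%. That is the SAP's rule; the protocol has no threshold.
- That subjects who leave because of a prohibited vaccine, or the Part B subset, fall under the same contradiction. The intercurrent event is AE discontinuation, and the estimand covers Part A.

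The reply does not remove the mismatch. Silence still means that following 7.2 to the letter loses an obtainable value. No rule makes an early EAP titer the primary value. Sensitivity analyses do not change what the primary analysis estimates. The SAP's MI is also a weak backstop as written: its predictors omit vaccination arm, and the Appendix 2 sample code averages over both arms, so it returns no GMT ratio.

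**Conclusion.** The point holds as a mismatch between the stated strategy and the data-collection rule, confined to Part A AE discontinuations before Visit 3 in subjects who would still agree to sampling. It is not evidence of a materially biased primary result. With one dose and a two-week window the loss is likely to be small. The 1.4% figure rests on two assumptions that the documents do not supply, a 2% excess loss in one arm and a 2-fold titer difference, and it ignores any part of that difference explained by the baseline-titer and age covariates. Power stays at 88.8% or above for losses up to 5%. The case for acting is that the repair is cheap and makes the reported estimand true to its label.

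**What to change.** 1. **Protocol 7.2:** ask Part A subjects who discontinue before Visit 3 and still agree to sampling to give the serum and nucleocapsid sample on days 12 to 16, at Visit 3 or at a concluding visit placed in that window. Nucleocapsid testing is named because it is not scheduled at EAP and the sensitivity analysis in 12.6.3 needs it.
2. **Protocol 12.6.1 and the SAP:** state that any titer drawn on days 12 to 16, including at an early EAP visit, is the Week 2 value in the primary analysis unless an infection or outside-booster exclusion applies.
3. **SAP 4.2.3.1 and Appendix 2:** replace the trigger of more than 5% with the protocol's rule of imputing any missing data. For that analysis to return a GMT ratio, the imputation model and code also need to carry vaccination arm.

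The cost is amendment wording; the visit and the blood tube are already planned. The downside is that the concluding visit may fall a few days later for some subjects. Where Visit 3 windows have already closed, item 1 recovers nothing, and only items 2 and 3 can take effect; they should be settled before unblinding.
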